3.3.2.2. Analysis Method

The null hypothesis is that there is a difference in ABR between the two prophylaxis regimens. The alternative hypothesis is that the two prophylaxis regimens are similar enough to be considered clinically equivalent.

The 90% 2-sided confidence interval (CI) for the mean difference in ABRs for the 2 prophylaxis regimens for ITT subjects will be constructed using the t distribution with n-1 degrees of freedom (n equals the number of subjects) to assess the equivalence of these 2 regimens. Equivalence will be demonstrated and the null hypothesis rejected if the limits of the 90% CI fall wholly within the interval of (-4, 4) bleeds per year. See Summary of Changes to Planned Analyses for the Final CSR (Item 4) for further discussion.

Additionally, an ANOVA model appropriate for the crossover design will be employed to test for the presence of treatment sequence, period and carryover effects. The ANOVA model will be fitted with terms for treatment sequence (AB or BA), treatment frequency (A or B), period (study segment 1 or 2), carryover and subject nested in treatment sequence. If one or more of the terms for treatment sequence, period or carryover are statistically significant then exploratory analyses may be prepared to help understand the nature of the effect. See Summary of Changes to Planned Analyses for the Final CSR (Item 6) for further discussion.

ABR will also be presented as descriptive statistics (n, mean, SD, median, interquartile range, minimum, and maximum). ABRs will be summarized by bleed type (ie, spontaneous or traumatic), by bleed location (eg, joint, soft tissue/muscle), and by treatment frequency (ie, prophylaxis A, prophylaxis B).

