## 22.5.3. Efficacy Variables

The annualized bleed rate (ABR) is the primary endpoint for testing the primary objective of the study, as well as for testing one of the secondary objectives of the study. ABRs will reflect the incidence of bleeds treated with FVIII replacement therapy. To avoid potential bias related to prior treatment, the first month of each protocol-defined prophylaxis treatment will serve as a washout period; ABR analyses will be performed with and without data from this washout period.

- For the primary objective of demonstrating that moroctocog alfa (AF-CC) prophylaxis reduces the ABR relative to on-demand therapy, the null hypothesis is that prophylactic treatment does not reduce the ABR relative to on-demand treatment. The alternative hypothesis is that prophylactic therapy does reduce the ABR.
- To test the hypothesis, an analysis of variance (ANOVA) will be conducted to compare the mean ABR between subjects in on-demand (segment 1) and prophylaxis (segment 2) treatment regimens. Only subjects who practice on-demand therapy with moroctocog alfa (AF-CC) during segment 1, before starting the protocol-defined moroctocog alfa (AF-CC) prophylaxis in segment 2, will be included in this analysis. The ANOVA will include factors for treatment regimen (study segment 1 or 2). The model will also include a blocking factor for subjects to ensure that the comparison of ABRs from each treatment regimen is performed on a within subject basis. The p-value for treatment regimen calculated in ABR of the ITT population will be used to test the null hypothesis; a p-value less than 0.05 will be considered significant.
- For the secondary objective of assessing the effect of a high- versus low-frequency dosing schedule on the efficacy of moroctocog alfa (AF-CC) prophylaxis, the null hypothesis is that there is a difference in mean ABR between the two prophylaxis regimens. The alternative hypothesis is that the two prophylaxis regimens are similar enough to be considered clinically equivalent. To test this hypothesis, the two protocol-defined prophylaxis regimens (a high- and a low-frequency dosing regimen) will be assessed in a crossover design. Only subjects who practice protocol-defined prophylaxis regimens in segment 1 and 2, respectively: the low- followed by the high-frequency dosing regimen (AB), or the high- followed by the low-frequency dosing regimen (BA) will be included in this analysis.

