1. The first interim CSR presented safety, efficacy and baseline data for subjects at Site PP separately from data for subjects at other sites, due to serious breaches of GCP compliance by the investigator and study staff at Site PP pertaining to data integrity. As implemented in the second Interim CSR, in the Final CSR, safety, efficacy and baseline summary data will be presented excluding Site PP with the exception of protocol deviations, recovery/pharmacokinetic data, and inhibitor incidence, which include all sites.

- 2. As determined for the second Interim CSR for the study's primary endpoint analysis in the OD cohort only, a linear mixed-effects model with unstructured variance-covariance matrix provides a more robust model for the comparison of annualized bleeding rate (ABR) given the nature of the study data, while still controlling for the same factors as specified in the SAP ANOVA model. This model allows for the inclusion of all intent-to-treat (ITT) subjects with ABR data and also takes into account the correlation between the 2 within-subject measurements of ABR at each segment. Because all enrolled subjects had severe (<1%) hemophilia at baseline (ie, just one level of the factor was present and therefore not informative), hemophilia severity is not included as a factor in the model as planned. In the Final CSR, the estimates of the ABR for each regimen (segment) and for the difference as well as the corresponding two-sided 95% confidence intervals (CIs) will be reported using the linear mixed-effects model described above rather than as described in SAP Section 3.3.1.2.

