1.4.2. Sample Size Estimation Comparing High versus Low Prophylactic Dosing

A secondary objective is to evaluate the effect of a high versus low dosing frequency schedule on prophylactic efficacy. Data from the previously mentioned moroctocog alfa study 301 revealed an ABR of 5.7 ± 5.2 (N=26) in subjects receiving a high-frequency prophylaxis regimen (3 infusions per week) compared to an ABR of 7.1 ± 4.1 (N=13) in patients receiving a lower-frequency prophylaxis regimen (2 infusions per week). Assuming an intraclass correlation of 30% and a standard deviation of 6 bleeds per year based on the above study results, a within-subject standard deviation of 5 bleeds per year was used for sample size calculations for the comparison between the high- and low-frequency prophylaxis regimens. Given this, 36 RP subjects are needed to provide 80% power to demonstrate equivalence of the two regimens. The two regimens will be considered equivalent if the limits of the 90% two-sided confidence interval for the difference in observed mean ABRs falls wholly within the interval of -4 to 4 bleeds per year. Allowing for an attrition rate of 25%, approximately 48 RP subjects should be enrolled to support this objective.

Based on a sample size re-estimation using data from this ongoing study, a difference of means of 1.3 bleeds per year between the two protocol-defined prophylaxis regimens (A and B) with a corresponding standard deviation of the difference of 6.5 was obtained requiring 38 subjects to provide 80% power to demonstrate equivalence of the two regimens. Allowing for an attrition rate of 30%, approximately 56 RP subjects need to be enrolled. The two prophylaxis regimens will be considered equivalent if the limits of the 2-sided 90% confidence interval for the difference in observed mean ABRs fall wholly within the interval defined by fewer than 4 bleeds per year. See the Summary of Changes to Planned Analyses for the Final CSR (Item 4) for further discussion.

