3.2. Analysis Populations

3.2.1. Intent-to-Treat Populations

The intent-to-treat (ITT) population includes all subjects for whom a legal acceptable representative has signed the informed consent/assent form. Screen failures will not be included in the ITT population. All safety and efficacy analyses will be performed on the ITT population.

The modified Intent-to-Treat (mITT) population is the subset of ITT subjects who received at least one dose of moroctocog alfa (AF-CC). Adverse events and lab data analyses will be additionally performed on the mITT population. Analysis of the incidence of confirmed FVIII inhibitor development will also be performed on the mITT population.

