3.3.2. Secondary Efficacy – Bleed Rate of High Frequency and Low Frequency Prophylaxis

Only RP subjects will be included in this analysis. Each RP subject will serve as his own matched control.

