3.3.2.1. Variable Definition

To assess the efficacy of routine prophylaxis, the ABR will be derived for each subject for each prophylaxis regimen by using the following formula:

ABR = number of bleeds / (Days on treatment regimen/365.25)

The number of bleeds for the ABR calculation includes all bleeds requiring treatment with a FVIII replacement product during the time on treatment. For segment 1 prophylaxis, days on treatment regimen for this calculation is defined as (date of visit 11 – date of visit 2) +1. For segment 2 prophylaxis, days on treatment regimen for this calculation is defined as (date of visit 19 – date of visit 11). If a subject does not complete a study segment, the days on treatment ends at the last study visit. The ABR will be calculated 3 ways: 1) including all data from the ITT population (all RP subjects), 2) including all data from the PR_A-PR_B population and 3) including all data from the PR_A-PR_B population except the first month of each segment (considering the first month to be a washout period and allowing for an analysis of the sensitivity of ABRs to previous therapy).

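### The RP equivalence decision is labelled ITT, but its interval can use only subjects with an ABR in both segments, so anyone lost before segment 2 drops out of it

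*SAP*

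**What the plan says.** **Decision rule.** SAP 3.3.2.2 bases equivalence on "The 90% 2-sided confidence interval (CI) for the mean difference in ABRs for the 2 prophylaxis regimens for ITT subjects", which "will be constructed using the t distribution with n-1 degrees of freedom (n equals the number of subjects"). SAP 3.3.2 adds: "Each RP subject will serve as his own matched control". Item 4 of the Summary of Changes narrows the margin from ±4 to ±3 bleeds per year and leaves the interval as it is.

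**Population.** SAP 3.2.1 states: "The intent-to-treat (ITT) population includes all subjects for whom a legal acceptable representative has signed the informed consent/assent form". Screen failures are removed. SAP 3.3.2.1 says that the first of its three ABR calculations covers all RP subjects, and gives a rule for incomplete segments: "If a subject does not complete a study segment, the days on treatment ends at the last study visit". Protocol 22.5.3 is narrower on who enters this comparison: "Only subjects who practice protocol-defined prophylaxis regimens in segment 1 and 2, respectively". SAP 3.5 imputes nothing unless otherwise specified. The supportive per-protocol set (SAP 3.2.2.2) also needs both segments.

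**Models that can use one segment.** Item 2 moves the on-demand (OD) comparison to a mixed model. The stated reason, repeated in Appendix C, is: "This model allows for the inclusion of all intent-to-treat (ITT) subjects with ABR data". Appendix C notes that this kept one subject who had only segment 1 at the data cut-off. Item 6 specifies a random-subject mixed model for the RP cohort, but introduces it as exploratory.

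**Size.** SAP 1.4.2 needs 38 subjects and continues: "Allowing for an attrition rate of 30%, approximately 56 RP subjects need to be enrolled".

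**The concern.** The label and the arithmetic disagree. A one-sample t interval on differences needs two ABRs per child. A child who withdraws before segment 2 has an ABR for the regimen he took, but the decision cannot use it.

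In an equivalence test the direction of the error matters. If the children who bled most on one regimen are the ones who leave, the remaining A−B difference can shrink toward zero, which favours the claim. The study is open-label, so families know the regimen.

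There is also a plausible occasion for leaving. A child escalated in segment 1 to 45 IU/kg every other day receives about 45 × 3.5 = 157.5 IU/kg per week. As written, he crosses at month 12 to a regimen of 45 × 2 = 90 or 25 × 3.5 = 87.5 IU/kg per week. This is noted only as a possible reason for withdrawal, not as a comment on dosing.

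**Working it through.** **1. The plan's own figure.** Inputs from SAP 1.4.2: true difference 1.3, SD of the difference 6.5, margin ±4, two one-sided 5% tests. A paired t calculation gives a smallest n of 38, with power 80.7%, which reproduces the plan. Then 38/0.70 = 54.3, so 55 against the stated figure of about 56. The sizing therefore also counts pairs only.

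**2. Ceiling on the loss.** 0.30 × 56 = 16.8, about 17 subjects, leaving 56 × 0.70 = 39.2 pairs. The 30% covers all attrition. The checks below use 17 (all of it before segment 2) and 8 (about half).

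**3. Loss unrelated to outcome.** There is no bias. The standard error is 6.5/√56 = 0.87 with all pairs and 6.5/√39 = 1.04 with 39. In a simulation with true difference 1.3 and margin ±3, keeping the one-segment subjects in a model moved the standard error from 1.03 to 0.97. Power rose from 48% to 51% with a sequence term, or 52% without.

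**4. Loss related to outcome, fixed numbers lost.** Simulation of 28 AB and 28 BA subjects, normal ABRs, SD 6 per segment and SD of difference 6.5, so the correlation is 1 − 6.5²/(2 × 6²) = 0.41. The true difference sits at the margin, so the nominal error is 5%. Ranges cover margins 3 and 4. The model has sequence, period and treatment with within-subject correlation, fitted to all subjects.

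| Who is lost before segment 2 | Lost | Paired: false equivalence (bias) | Model: false equivalence |
|---|---|---|---|
| Random | 17 | 5.0% (0.0) | 4.9–5.0% |
| Random | 8 | 4.6–4.8% (0.0) | 4.7–4.8% |
| High segment 1 ABR, either sequence | 17 | 5.8–6.5% (−0.1) | 4.8–4.9% |
| High segment 1 ABR, either sequence | 8 | 5.9–6.1% (−0.1) | 4.5–5.0% |
| High segment 1 ABR, A starters only | 17 | 14.5–18.8% (−0.6 to −0.8) | 4.8–5.2% |
| High segment 1 ABR, A starters only | 8 | 11.0–14.9% (−0.4 to −0.6) | 4.8–5.3% |
| Worse on A than B (unobserved), A starters only | 17 | 29.9–30.1% (−1.2) | 40.2–41.1% |
| Worse on A than B (unobserved), A starters only | 8 | 20.1–21.7% (−0.7 to −0.8) | 18.1–18.5% |

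The A-starter rows are lopsided by construction: 17 of 28 is 61% of that sequence and 8 of 28 is 29%, with no losses in the other sequence. Across all runs, the highest value for equal outcome-related loss was 7.5%.

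**5. Loss by a threshold rule.** Here ICC is 0.3, per-segment SD is √(6.5²/1.4) = 5.49, the margin is ±3 and the true difference is 3. A starters with segment 1 ABR above 12 leave with the stated probability; everyone else leaves with probability 15%.
- Regimen A mean 10.2, 90% of high bleeders leave: 29% lost overall (43% of A starters, 15% of B starters), paired mean 2.2, false equivalence 18–19%.
- Regimen A mean 7.1 (the low-frequency figure from the earlier study in SAP 1.4.2), 90% leave: 22% lost, paired mean 2.5, false equivalence 13–13.5%.
- Regimen A mean 7.1, 50% leave: 7.5–7.7%.
- The same kind of rule on both regimens (75% of high bleeders, 12% of others): 6.6–6.8%.

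**6. Where the mixed model fails.** If 90% against 15% withdrawal depends on the child's stable underlying bleeding level, in BA starters, with true difference 3, the paired mean is 2.98 and false equivalence 5.1%. The model gives about 2.5 and 12–12.5%. With AB starters instead, the model is biased upward, to 3.47.

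**7. Requiring both.** The chance that both intervals show equivalence cannot exceed the smaller of the two rates. That is at most 5.3% for loss driven by segment 1 ABR (step 4) and at most 5.1% for the stable-level case (step 6). For loss driven by the unobserved difference the bound is still 18–30%.

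**The case against.** Several stronger readings are tempting, and the documents do not support them.

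- **That 17 children will be excluded.** The 30% is total attrition. A child who leaves during segment 2 stays in with a shorter, annualised segment, so this is not strictly a completers' analysis.
- **That the test runs at 18–19%.** That needs loss concentrated in one regimen, with most high bleeders leaving. No passage gives such an imbalance. Under the threshold rule it also needs a Regimen A mean near 10.2; at 7.1 with half the high bleeders leaving, the figure is below 8%.
- **That the step down at month 12 creates the imbalance.** It applies to both sequences. Unless escalation rates differ greatly between regimens, it belongs with the equal-loss cases at about 6–7.5%.
- **That the restriction is concealed.** Protocol 22.5.3 states it, SAP 3.3.2 calls each subject his own control, and SAP 1.3.4 counts evaluable subjects who practised both segments. The Protocol 22.5.3 sentence could even be read as merely selecting the RP cohort, but the n-1 interval on differences imposes the restriction either way.
- **That the mixed model should simply replace the paired interval because it assumes less.** Step 6 refutes this. Paired differences cancel a child's stable bleeding level and the model does not, while the model handles loss driven by observed segment 1 ABR. Neither assumption contains the other.

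The plan is also not empty here. Item 6 will estimate a treatment effect with a random-subject model, and SAP 3.1 summarises discontinuation reasons. But Item 6 does not enter the decision, SAP 3.1 does not ask for reasons by sequence, and no withdrawal sensitivity analysis is specified for this comparison. What stands is the mismatch between label and analysis, and a decision that rests on one missing-data assumption with no planned check.

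**Conclusion.** The concern holds in a limited form. The interval that decides RP equivalence is called ITT but excludes every randomised subject without a segment 2 ABR. At most about 17 of 56 are affected; the true number is unknown.

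The consequence depends on why they leave. Random loss costs a little precision. Outcome-related loss that is equal on both regimens moves false equivalence from 5% to about 6–7.5%. Loss of high bleeders mainly from one regimen could move it to about 8–19%. These figures rest on normal ABRs, SD of difference 6.5, and assumed means and withdrawal patterns that the documents do not supply for this trial. They show what could happen, not what is expected.

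The point should be corrected: the sponsor accepted the principle for the OD cohort, and the RP model is already written. It does not by itself invalidate the comparison.

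**What to change.** In SAP 3.3.2.2, before the RP data are locked:

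1. Report the 90% interval for A−B from the Item 6 model (sequence, period, treatment, random subject), fitted to all RP ITT subjects with an ABR in at least one segment, as the ITT result judged against the margin.
2. Keep the paired interval beside it, labelled as the both-segments analysis, and require equivalence to hold in both.
3. Reconcile the inclusion sentence in Protocol 22.5.3 with the all-RP-subjects wording in SAP 3.3.2.1.
4. Tabulate by sequence the subjects withdrawn before segment 2, with segment 1 ABR, escalation status and reason.
5. Add one missing-not-at-random sensitivity analysis, for example shifting the unobserved segment 2 ABRs until the conclusion changes. Step 7 shows that requiring both intervals does not cover this case.

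The cost is SAP wording, one more decision analysis, one sensitivity analysis and one table. No new data are needed. The equivalence claim becomes slightly harder to meet, and power at ±3 on the plan's own inputs is already only about 47% with 38 pairs.

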The 90% 2-sided confidence interval (CI) for the mean difference in ABRs for the 2 prophylaxis regimens for ITT subjects will be constructed using the t distribution with n-1 degrees of freedom (n equals the number of subjects) to assess the equivalence of these 2 regimens. Equivalence will be demonstrated if the limits of the 90% CI fall wholly within the interval of (–4, 4) bleeds per year.

• ABR will also be presented as descriptive statistics (n, mean, SD, median, minimum, and maximum). ABRs will be summarized by bleed type (ie, spontaneous or traumatic), by bleed location (eg, joint, soft tissue/muscle), and by treatment period (ie, on-demand therapy or prophylaxis).

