- 6. For the exploratory analysis in RP cohort subjects, to test for the presence of treatment sequence, period and carryover effects, SAP Section 3.3.2.2 states that the ANOVA model will be fitted with terms for treatment sequence (AB or BA), treatment frequency (A or B), period (study segment 1 or 2), carryover and subject nested in treatment sequence. However, this model is overparameterized. Instead, the more appropriate mixed-effect model ABR=sequence period treatment, with subject as a random effect will be used to evaluate the treatment effect. Contrasts will be constructed to test if the carryover effect for each sequence is the same, and if the same, if that carryover effect is equal to zero.
- 7. Protocol Amendment 10 has text in section 15.2 (also appears in SAP Section 2.2) which states that the pharmacokinetic dose will be prepared from a single lot. However, multiple lots were used over the course of this study.
- 8. Protocol Amendment 10 has text in sections 22 and 22.6 (also appears in SAP Section 3) which indicates that both efficacy and safety will be reported separately for the 2 cohorts (OD and RP). However, only efficacy data is presented separately, and safety data is presented for all subjects combined.

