3.2.2.2. Prophylaxis Regimens Per-Protocol Population

For the analysis comparing the two moroctocog alfa (AF-CC) prophylaxis regimens (A and B), the per-protocol population (herein referred to as the PR_A-PR_B population) consists of the subset of RP subjects who have no major protocol violations (see SAP Section 3.7.1) and who practice protocol-defined prophylaxis during segment 1 and during segment 2. An interruption in treatment due to any unplanned and required surgery will not necessarily disqualify the subject from the PR_A-PR_B population, but the time on surgery will not count towards the time on treatment in either segment. If a subject requires a dose escalation, only

the data from the time on the originally prescribed regimen will be used. The first month of each segment will be considered a washout period. Analyses will be performed with and without data from the washout periods in order to assess and minimize the effect of the previous treatment regimen on ABR. Note: If a RP subject develops a confirmed FVIII inhibitor, his data will be included up to the time an inhibitor is determined to be present.

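### The RP equivalence interval ignores period although a period-adjusted model is already planned; its ITT label does not fit, and the zero-carryover contrast can only test period

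*SAP*

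**What the plan says.** Protocol 22.5.3 and SAP 3.3.2.2 rest the regimen comparison on a 90% two-sided interval "for the mean difference in ABRs for the 2 prophylaxis regimens for ITT subjects". SAP 3.3.2.2 says it "will be constructed using the t distribution with n-1 degrees of freedom (n equals the number of subjects". Neither period nor sequence appears in it. Item 4 of the SAP's Summary of Changes narrows the margin from (-4, 4) to (-3, 3) and leaves the method alone.

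SAP 3.3.2.2 adds an ANOVA for sequence, period and carryover. If one of these is significant, "then exploratory analyses may be prepared to help understand the nature of the effect". Item 6 replaces that ANOVA. It opens "For the exploratory analysis in RP cohort subjects" and states that "the more appropriate mixed-effect model ABR=sequence period treatment, with subject as a random effect will be used to evaluate the treatment effect". It then plans contrasts for whether carryover is the same in the two sequences, "and if the same, if that carryover effect is equal to zero". Nothing connects this model to the equivalence decision.

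On the analysis set, SAP 3.3 and 3.3.2.2 say ITT, and SAP 3.3.2.1 equates ITT with all RP subjects. Protocol 22.5.3 limits the analysis: "Only subjects who practice protocol-defined prophylaxis regimens in segment 1 and 2, respectively". The per-protocol set in SAP 3.2.2.2 carries a near-identical condition, "and who practice protocol-defined prophylaxis during segment 1 and during segment 2", along with further exclusions.

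**The concern.** An AB/BA design protects the treatment comparison from a time trend only if the two sequences carry equal weight. A one-sample t on all A-B differences weights the sequences by how many subjects completed in each. The subjects are children followed over two 12-month segments, the trial is open-label, and 30% attrition is allowed for, so neither a stable bleed rate nor equal completion by sequence can be taken for granted. A trend combined with unequal completion shifts the estimate. False equivalence then rises at the margin the shift pulls the estimate inward from, and falls at the other. An adjusted estimate will be reported alongside but cannot change the conclusion.

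Two further points follow. A reader told that the interval is ITT will assume every randomised RP subject contributes, which a within-subject difference does not allow. And a contrast presented as a test of zero carryover may lead an ordinary period effect to be reported as carryover.

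**Working it through.** **Inputs from the documents.** True difference 1.3, SD of the difference 6.5, 38 evaluable, 56 enrolled, 30% attrition (SAP 1.4.2); 90% interval (SAP 3.3.2.2); margin 3 (Item 4) or 4 (SAP body); 1:1 allocation (SAP 1.3.3).

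**Assumed, because the documents give neither.** Period difference p (segment 2 minus segment 1) of 1, 2 or 3 bleeds/year, and the completer split by sequence.

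**Plan's own figure.** Paired t with 37 df, margin 4, difference 1.3, SD 6.5, n = 38: power 80.7%. The stated 38 for 80% reproduces, as an analysis of subjects with both segments.

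**Bias.** With true A-B difference d, the expected difference is d - p in AB and d + p in BA. Hence:
- Paired t: mean = d + p(nBA - nAB)/n. At a 22:16 split the size is 6/38 × p = 0.16, 0.32, 0.47 for p = 1, 2, 3.
- Adjusted: the average of the two sequence means is [(d - p) + (d + p)]/2 = d, with pooled variance and n-2 = 36 df.

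**False equivalence, true difference 3, margin 3** (simulation; 6.5 taken as the SD within sequence; direction in which the bias pulls the estimate inward):

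| Split | p = 1 | p = 2 | p = 3 | Adjusted |
|---|---|---|---|---|
| 19:19 | 4.8% | 4.3% | 3.5% | 5.0% |
| 20:18 | 5.3% | 5.2% | 4.8% | 5.0% |
| 21:17 | 5.8% | 6.4% | 6.5% | 5.0% |
| 22:16 | 6.5% | 7.7% | 8.5% | 5.0% |

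With the opposite sign of p, 22:16 gives about 3.4, 2.2 and 1.2%.

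**How likely is imbalance?** If 28:28 are randomised and 38 complete at random, the split is hypergeometric: 39% chance of 21:17 or worse, 15% of 22:16 or worse. Weighted over all splits, the paired t gives 4.9, 4.5 and 4.0% at a fixed margin. A 22:16 split corresponds to 22/28 = 79% against 16/28 = 57% completing.

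**Power at true difference 1.3, margin 3.**
- 6.5 as the within-sequence SD: at 19:19, 45.8/43.3/39.3% for p = 1/2/3 against 46.5% adjusted. At 22:16 with p = 2, 53.7 or 32.8% by sign against 45.6% adjusted.
- 6.5 as the raw paired SD: the within-sequence SD is sqrt(6.5² - 4p²f(1-f)n/(n-1)), where f is the share in AB, giving 6.42/6.18/5.75 at 19:19. Power there is 46.6/46.7/46.8% against 47.4/50.2/55.6% adjusted. At 22:16 with p = 2, it is 58.1 or 35.2% against 49.2%, and false equivalence is 7.8%.

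**Analysis set.** Each RP subject is his own control (SAP 3.3.2) and missing data are not imputed (SAP 3.5), so a subject with segment 1 only has no A-B difference. At most 0.30 × 56 = 16.8, about 17 subjects, are affected, if all attrition falls in segment 1. Adding 17 such subjects to 39 completers in a mixed model with equal-variance weights reduces the variance of the A-B estimate by 10.6/7.6/4.6% (assumed intraclass correlation 0.30/0.50/0.70) if their ABRs are as precise as the others'. If their within-subject variance is four times larger, the change is -4.9/-0.3/+1.7%, where a negative sign means a wider interval. Short exposure makes this a real possibility: SAP 3.3.2.1 sets no minimum time, and one bleed in 10 days gives 1/(10/365.25) = 36.5 bleeds/year.

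**Carryover.** With period effect π and common carryover λ, the cell means are:
- AB: segment 1, μ + A; segment 2, μ + π + B + λ
- BA: segment 1, μ + B; segment 2, μ + π + A + λ

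π and λ occur only as π + λ; mean, period, treatment and common carryover have rank 3 of 4. The zero-carryover contrast therefore cannot be separated from a period test. Unequal carryover shows only in the difference between sequence totals, where it cannot be told from a sequence effect or a treatment-by-period interaction.

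**The case against.** The harm depends on two quantities the documents do not supply. Without sequence-related dropout, the planned rule averages 4.9, 4.5 and 4.0% false equivalence, so it controls error before the split is known. The same imbalance with the opposite trend is conservative. A bias of 0.16 to 0.47 is small beside a standard error of about 6.5/√38 = 1.05. The adjusted estimate will be reported anyway. The paired t is stated consistently in both documents and matches the sample-size basis. All of this stands, and it is why the point is an improvement to make and not a fatal flaw.

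Changing the decision estimator late in an open-label trial, after an A-B difference of 1.3 has been seen, carries a credibility cost. Naming the adjusted interval as a sensitivity analysis would avoid that cost and expose any discrepancy, but would leave the decision on the estimate that depends on the split. The cost stands as a reason for a written justification before the final analysis.

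The sentence in protocol 22.5.3 can be read as naming the RP cohort and not its completers. That does not rescue the label: on either reading a one-segment subject yields no difference. The ITT set is still not the per-protocol set, which also removes major violators and post-escalation data.

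A very short segment 2 can also produce an extreme ABR among subjects with both segments. That is true under the planned paired t as well, so it does not separate the two estimators.

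The carryover contrast sits in an exploratory model and its coefficients are not written out. It does not affect the decision, but the algebra leaves it no other meaning.

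**Conclusion.** All three parts hold. The decision interval omits period in a design randomised by sequence, while the SAP keeps the period-adjusted model as exploratory. With balanced completers the consequence is at most mild conservatism, or a forgone gain in precision if 6.5 is the raw paired SD. At an assumed 22:16 split and period differences of 1 to 3 bleeds/year, false equivalence is 6.5 to 8.5% at one margin against 5.0% adjusted, and power at p = 2 moves to 53.7 or 32.8% against 45.6%. The error is systematic only if dropout differs by sequence. These figures assume normal differences with equal variance in the two sequences. The ITT label is wrong as written, and the zero-carryover contrast is a period test whatever the effect sizes. The change should be made.

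**What to change.** - **Decision interval.** In protocol 22.5.3 and SAP 3.3.2.2, take the 90% interval for A-B from a model with fixed sequence, period and treatment and subject effects, in RP subjects with an ABR in both segments. This equals the average of the two sequence mean differences with pooled variance and n-2 df. Keep the paired t as a sensitivity analysis.
- **Label.** Replace ITT and all RP subjects for this comparison (protocol 22.5.3; SAP 3.3, 3.3.2.1 and 3.3.2.2) with a name for that set, and report randomised subjects omitted, by sequence.
- **One-segment subjects.** Fit the Item 6 model to all RP subjects with an ABR in either segment as a sensitivity analysis only, because no minimum exposure is set.
- **Carryover.** Delete the zero-carryover contrast. Report the equal-carryover contrast as confounded with sequence and with treatment-by-period interaction.
- **Timing.** Make the change, with a dated reason, before the final analysis.

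Cost: wording only, since the model is already planned. With no period effect, the power loss at margin 3 is essentially nil at 19:19, 0.9 points at 22:16 (46.6 against 45.7%), 0.4 averaged over random splits, and 2.7 at 24:14; a split that uneven or worse has a 0.9% chance.
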